In this trial, please report the serious adverse event report to the National Medical Products Administration, the National Health and Family Planning Commission in a timely manner according to the following contact information, and notify the research institution regularly.

The investigator must complete a Serious Adverse Event Report Form, and should record the time, the way, and to whom to report the serious adverse events in the original data. The sponsor guarantees it to satisfy all reporting requirements of laws and regulations.

The institute to report	Contact department /person	Telephone
National Medical Products Administration (NMPA)	Registration department	[name]/[name]
Institute of clinical blood transfusion, Guangzhou Blood Center	[name]	[name]

In case of any serious adverse event unrelated to the trial method, the researchers shall withdraw from the clinical trial when they think it is necessary or the subject or his legal guardian requests to withdraw from the trial, and the withdrawal case shall complete the last laboratory examination.

(V) Follow-up of the adverse events

All adverse events should be followed up to the normal or baseline level, or the investigator can reasonably explain the abnormality and think that no follow-up is necessary to ensure the safety of the subjects. According to the type and severity of the adverse reactions, the follow-up methods can be selected as inpatient, outpatient, home visiting, and telephone visiting and other ways.

X. Quality control of the clinical trial

(1) Quality control measures

Both the sponsor and the investigator should adopt Standard Operating Procedure (SOP) to ensure the quality control and the implementation of quality assurance system of the clinical research. All the observation results and findings in the clinical research should be verified to ensure the reliability of the data and the conclusions in the clinical research origin from the original data. Quality control must be adopted at every stage of data processing to ensure that all data are reliable and processed correctly.

(II) Training of researchers

Before the formal starting of clinical research, the responsibility and attitude of the researchers participating in the clinical research must be emphasized firstly. The person in charge of the trial shall train the researchers on the experimental scheme, unify the understanding, be familiar with the collection methods and procedures, and understand the special requirements of the research project, so as to improve the internal observation consistency and inter observer consistency of the clinical research data collectors and ensure the reliability of the research conclusion. At the same time, the researchers are required to strictly implement SOP in the whole process of clinical research to ensure the implementation of quality control measures in clinical research and improve the quality of clinical research and case report form.

(III) The measures to improve patients' compliance

1. The investigator should carefully implement the informed consent of transfusion treatment to make the patient or his legal guardian fully understand the requirements of the trial and cooperate well. The sponsor provides free trial intervention and related laboratory tests.

2. To monitor the compliance of the patient during the trial.

(IV) The monitoring of clinical research

The sponsor authorizes Guangzhou Haibote Pharmaceutical Technology Co., Ltd. to appoint qualified supervisors to conduct regular on-site monitoring visits in the experimental hospitals to ensure that all contents of the research plan are strictly observed and the original data are checked to ensure that they are consistent with the contents on the CRF. The appointed supervisor shall carry out the audit according to the requirements of GCP, and write the audit report, which includes:

1. Whether the clinical trial institute has appropriate conditions;

2. The patient's informed process complies with the declaration and regulations of Helsinki;

3. The implementation of the trial plan;

4. The protection measures for patients during the trial;

5. To confirm that all data records and reports are correct and complete;

6. To confirm that all adverse events are recorded and serious adverse events are reported and recorded within the specified time;

7. To verify that the test method is carried out in accordance with the relevant laws and regulations, and have the corresponding records;

8. Including the supervision date, time, the name of the supervisor, the problems found during the supervision and handling methods, etc.

(V) The inspection of clinical research

The clinical trial supervision and management department and the sponsor could authorize the auditors to carry out systematic inspection on the clinical study to determine whether the implementation of the trial is consistent with the trial scheme and whether the reported data is consistent with the records of all clinical participating institutes, that is, whether the data reported or recorded in the case report form is the same with the medical record or other original records. The audit shall be performed by the person not directly involved in the clinical study.

XI. Data management

(I) Data entry and modification

The leading institute of the trial is responsible for the data entry and management. For the questions in the case report form, the data manager will send the questions to the researcher through the supervisor, and the researcher shall answer and return them as soon as possible. The data manager will modify, confirm and input the data according to the researcher's answers, and send the DRQ again if necessary.

(II) Data locking

After all doubts are solved and the established database is confirmed to be correct, the data manager should write the data management audit report and lock the audited data. The locked data file and statistical plan will not be changed.

XII. Statistical analysis

(I) The population for statistical analysis

The population for analysis includes safety analysis set (SS) and full analysis set (FAS).

1. The Safety analysis population: the subjects receiving at least one time of blood transfusion.
2. Full analysis population.

(II) Statistical analysis method

1. Demographic data and baseline analysis

* Analysis according to FAS;

- * Descriptive demographic data and other baseline characteristic values;
- * To calculate the number of cases, mean value, standard deviation, median, minimum and maximum for the continuous variables;
- * To calculate the frequency for the count and grade data.

2. Safety analysis

The SS population was used for safety analysis, and safety indexes included adverse events, laboratory examination, vital signs, etc. To summarize the data by stages and units. The adverse events will be aggregated.

* Adverse events

All adverse events will be coded with MedDRA.

According to NCI CTCAE V5.0, the incidence (frequency) and severity distribution of AE, TEAE, SAE and AESI were summarized according to SOC and PT in MedDRA code.

The subjects who terminated the treatment due to the adverse events, the subjects who had SAE and the dead subjects will be listed (at least including the start date, end date, severity, relationship with trial intervention, measures taken, outcome of AE).

* Laboratory examination

Blood routine and biochemical indexes were used to describe the measurement value and change value before and after treatment with mean \pm standard deviation, maximum value, minimum value and median. And the normal and abnormal changes before and after treatment were described with cross classification table.

Urine routine: use cross classification table to describe the normal and abnormal changes before and after treatment.

The proportion of the subjects with abnormal and clinically significant changes will be described, in which whether the abnormal has clinical significance is judged by the researchers.

The list of subjects with abnormal changes (with or without clinical significance) after treatment.

* ECG examination

Descriptive statistical ECG indicators compared with the baseline changes, using a cross classification table to describe the normal and abnormal changes before and after treatment, and a list of data will be provided.

* Vital signs, physical examination and other safety related examinations

The examination results of vital signs and changes compared with the baseline will be described statistically.

The subjects with abnormal changes in physical examination compared with baseline were described in the form of list.

(III) The software for analysis

SAS9.4 is used for the statistics analysis of the general data.

XIII. Preservation of the original data

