In recent years, more and more experimental and clinical data show that the most common "Asia type" DEL in Asian populations has the characteristics of "complete DEL". First, in several independent studies, the adsorption/elution experiments did not detect the absence of D antigen determinant in "Asia type" individuals [2, 14]. In addition, the synonymous mutation in exon 9 of the *RHD* gene (c.1227G>A, p.K409K) defined the "Asia type" DEL allele have been shown to cause abnormal mRNA splicing in molecular mechanisms studies. It resulted in a series of abnormal mRNA transcripts lacking exon 9, but further Mini Splicing function analysis in vitro found that the "Asia type" DEL allele express extremely low abundance transcripts including complete exon 9. This transcript may express a very low density of normal D antigen, thus forming the "Asia type" DEL phenotype [15]. Most importantly, several prospective and retrospective studies on observation of "Asia type" DEL pregnant women have shown that none of them developed alloanti-D. These studies involved the data from at least a thousand of "Asia type" DEL pregnant women (including more than 600 cases studied in our study and hundreds of samples included in several other studies) [6, 13, 16, 17] in China, which covering more than one million of people. In contrast, in the true D- Chinese population excluding "Asia type" DEL, the frequency of alloanti-D immunity ranges from 8.5% to 40% [13, 17]. Therefore, clinical data show that in the case of "Asia type" DEL Chinese pregnant women with high probability of having a normal RhD-positive fetus (>95%), alloanti-D will not be produced by D+ red blood cells from the fetus and newborn during pregnancy and childbirth.

Based on the results of previous research, it is extremely urgent to conduct a clinical trial of D+ blood transfusion in "Asia type" DEL patients, and to follow up in detail to obtain the anti-D immunization data in transfusion patients. This study is essential to set up a new blood transfusion strategy for "Asia type" DEL patient. In South Korea, two cases of "Asia type" DEL patients have been reported to receiving D+ blood transfusion, but still lacking of systematic clinical trial data to make the conclusion [18]. Therefore, the Korean National Blood Transfusion Guidelines (KNGBT) concludes that now there is not enough direct evidence to prove the safety of "Asia type" DEL

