patients receive D+ blood transfusion, and D+ blood transfusion is only allowed in the condition of emergency or lacking of D- blood supply for "Asia type" DEL patients [18]. In summary, this clinical study has important practical significance and can provide basic evidence whether anti-D alloimmunization will occur in "Asia type" DEL patients with ordinary D+ blood transfusion. If a new strategy of D+ blood transfusion in "Asia type" DEL patients can be established in the future, that is, the routine "Asia type" DEL testing in patients with a primary D- phenotype could be performed, and then to treat the "Asia type" DEL patients as ordinary D+ patients, rather than the rare D- patients in clinic. It will save at least 25% of rare D- blood in East and Southeast Asian countries, and it will also prevent "Asia type" DEL pregnant women receive anti-D immunoglobulin injection and other medical intervention/monitoring to prevent anti-D associated fetal neonatal hemolytic disease, which also could save the precious blood product anti-D immunoglobulin that derived from the sera from the D- volunteers who are sensitized.

II. Purpose of the trial

To explore the safety and effectiveness of RhD+ blood transfusion in Chinese "Asia type" DEL patients to lay the foundation for establishing a new blood transfusion strategy for "Asia type" DEL patients.

III. Design of the trial

The aim of this study is to analyze whether anti-D alloimmunization will occur in "Asia type" DEL patients after D+ blood transfusion, and then to compare the results with the data from the true D- patients received D+ blood transfusion to determine the "Asia type" DEL patients should be treated as D+ or D- patients in the future. The ideal study control group is the incidence of anti-D alloimmunization of true D- patients receiving D+ blood transfusion. But for ethical reasons (according to the requirements of *Technical Specifications for Clinical Blood Transfusion*, true D- patients can only be transfused with D+ blood in urgent situation or lacking of D- blood supply), and it is not appropriate to set up the control group (to transfuse D+ blood in true D- patients in non-emergency situations). Although the summarized rate of alloanti-D occurrence (22.9%, 53/231) [19-22] in true D- patients transfused with D+ blood in previous reported studies could be used as the control for the statistical analysis including sample size calculation, our study could not satisfy

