the demands as the “Asia type” DEL transfusion satisfied the inclusion criteria belong to a rare event because of the rare distribution of “Asia type” DEL in our population (0.75-1‰). In theory, more than 2000 “Asia type” cases receiving D+ blood transfusion, which covering around fifty millions population, are necessary to compare the difference of alloanti-D occurrence between the “Asia type” DEL patients group in our study and the true D- control patients group with similar disease categories receiving D+ RBCs transfusion. It is not feasible in practice for this study.

Therefore, a multi-center, single-arm clinical trial was performed in this study. When any hospital in Guangzhou city applies for D- blood supply in a non-emergency situation, routine “Asia type” DEL typing, antibody screening and identification, and cross-matching test for “Asia type” DEL patients were conducted in the reference lab of Guangzhou Blood Center. The “Asia type” DEL patients meeting the inclusion criteria were recruited in each cooperative hospital. After the informed consent for D+ blood transfusion was obtained from the patient or family members, cross-matched D+ blood was provided by Guangzhou Blood Center. D+ blood transfusion was performed at the corresponding hospital according to *Technical Specifications for Clinical Blood Transfusion* [23] and *Technical Guidelines for Vaccine Clinical Trials* [24].

IV. Selection of Subjects

(I) Inclusion criteria (same to the Protocol Abstract)

(II) Exclusion criteria (same to the Protocol Abstract)

(III) Rejection criteria

1. Cases that did not meet the inclusion criteria or belong to one of the exclusion criteria after enrollment;
2. Cases who did not receive blood transfusion finally in clinic after enrollment.

(IV) Dropout criteria

1. All patients, who signed the informed consent of blood transfusion, meet the inclusion criteria and enrolled, but failed to complete the follow-up observation in accordance with the protocol requirements;
2. The subject requested to withdraw from the trial;

3. In the trial, if the subject has an adverse event that prevents him/her from completing the clinical trial, the investigator should record the process and outcome of the adverse event in detail, and make a judgment on the cause and effect of the trial. Cases dropout due to adverse events should be included in the statistical analysis of adverse events, but were not included in the evaluation of efficacy;

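### The figure of more than 2000 cases has no stated inputs and does not follow from the rates the plan cites, and anti-D incidence has no planned interval or historical comparison

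*Combined protocol and SAP*

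**What the plan says.** Section III (Design of the trial) states that the study will establish whether anti-D appears after D+ transfusion and then "to compare the results with the data from the true D- patients received D+ blood transfusion", in order to decide how these patients should be handled in future. A concurrent control is ruled out on ethical grounds. The section names a substitute, "the summarized rate of alloanti-D occurrence (22.9%, 53/231) [19-22] in true D- patients transfused with D+ blood in previous reported studies", and accepts that this published figure "could be used as the control for the statistical analysis including sample size calculation".

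It then says the study cannot meet that demand because eligible DEL transfusions are rare, and adds: "In theory, more than 2000 “Asia type” cases receiving D+ blood transfusion, which covering around fifty millions population, are necessary to compare" alloanti-D occurrence with "the true D- control patients group with similar disease categories receiving D+ RBCs transfusion". The conclusion is "It is not feasible in practice for this study".

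Section I supplies the other rates. Studies of DEL "pregnant women have shown that none of them developed alloanti-D", in at least a thousand pregnancies, while in true D- Chinese people "the frequency of alloanti-D immunity ranges from 8.5% to 40" per cent.

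The Protocol Abstract fixes no sample size and makes the analysis descriptive, with frequency and percentage for categorical variables. Anti-D incidence heads the list of safety indices in the Abstract and in sections VI(III) and VII(II). Section VIII schedules antibody screening at all three post-transfusion phases. Section XII(II) does not name anti-D; its laboratory part covers blood routine, biochemistry and urine.

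**The concern.** A required sample size has meaning only with its inputs, and none is given here. Of the rates the plan cites, the most direct contrast is 22.9% against a rate it argues is close to zero. That is a large difference, which ordinarily needs tens of patients per group.

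The number matters because it is part of the reason for dropping a comparison that the same section calls possible and includes in the aim. What suffers is that rationale and the anti-D analysis, not the single-arm design or recruitment.

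With no fixed N, the width of the interval is the main thing a reader needs. If no patient forms anti-D, the estimate is 0% whether 15 or 60 patients were tested, and only the upper bound shows which rates have been excluded. The plan does not commit to reporting it. Section XI(II) says the statistical plan will not change after lock, so the gap has to be closed before then.

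**Working it through.** **Trying to reproduce the plan's figure.** Section III gives no inputs for 2000, so it can only be approached from the rates cited.

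**Inputs from the protocol**
- Control rate 53/231 = 0.2294 (section III); exact 95% CI 17.7% to 28.9%.
- True D- range 8.5% to 40% (section I; not given as transfusion rates).
- No anti-D in at least a thousand DEL pregnancies (section I; not transfusion evidence).

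**Assumptions, because the protocol is silent:** DEL rate p1 = 0, 1, 2 or 5%; two-sided alpha 0.05; 80% or 90% power; equal groups.

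**Formula**, with p̄ = (p0 + p1)/2:

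n per group = [1.960·√(2p̄(1−p̄)) + z_power·√(p0(1−p0) + p1(1−p1))]² / (p0 − p1)²

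**One case in full:** p0 = 0.2294, p1 = 0, 80% power (z = 0.842).
- p̄ = 0.1147; the two terms are 0.883 and 0.354.
- (0.883 + 0.354)² / 0.2294² = 1.531 / 0.0526 = 29.1, so 30 per group.

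**All cases, n per group at DEL rates 0 / 1 / 2 / 5%**

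| Control rate | 80% power | 90% power |
|---|---|---|
| 22.9% | 30 / 34 / 38 / 58 | 39 / 44 / 51 / 77 |
| 17.7% (lower limit of 53/231) | 40 / 47 / 56 / 97 | 53 / 62 / 74 / 130 |
| 8.5% | 88 / 126 / 184 / 806 | 117 / 167 / 246 / 1078 |
| 40% | 15 / 16 / 17 / 22 | not needed |

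Against 22.9% at 80% power, 2000/58 = 34 and 2000/30 = 67.

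**Stricter settings.** With two-sided alpha 0.01, 90% power and a continuity correction, equal groups against 22.9% need at most 120 each. For 8.5% against 5% the same settings give 1584 each.

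**Working backwards.** For 2000 per group the DEL rate would have to be 19.3% (80% power) or 18.8% (90%) against 22.9%, or 6.2% or 5.9% against 8.5%. Neither fits the near-zero rate the protocol argues for.

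**Using the 231 historical patients as the control.** With Fisher's exact test and both sides treated as random, 80% power is first reached at n = 15, 17, 24 and 37 DEL patients for DEL rates of 0, 1, 2 and 5%. Exact power is not monotone: at a 1% rate it is 0.81 at n=17, 0.77 at n=18, 0.79 at n=19 and 0.81 again at n=20. Example results against 53/231: 0/15 gives p=0.046, 0/20 gives p=0.010, 1/23 gives p=0.035.

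**What zero events would show.** The two-sided exact 95% upper bound is 1 − 0.025^(1/n):
- n=15: 21.8%
- n=30: 11.6%
- n=60: 6.0%

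**The case against.** **An underived number is not a proven error.** The sentence refers to controls in similar disease categories, which may mean a matched or stratified comparison rather than one against the pooled 22.9%. This stands in part: the figure is unsupported, not impossible. But no strata, matched rates, ratio or margin is stated, so the wording cannot justify 2000.

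**Equal groups are my assumption.** With fewer controls than cases the number rises. For 8.5% against 5% at 90% power, one control per two DEL cases needs about 1,590 DEL cases, and one per four about 2,600. So 1078 is not a ceiling. It remains a corner case: against 22.9%, at 90% power, even one control per ten DEL cases needs only about 130 to 350.

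**About 2000 does arise for other aims.** A one-point non-inferiority margin at 1% rates needs 2081 per group at 90% power, and zero events in 1996 patients puts the one-sided 95% upper bound at 0.15%. Section III describes neither aim.

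**Rarity is the direct reason given, with 2000 as an illustration.** True, and neither rarity nor the ethical argument is disputed. Removing the figure would leave the design unchanged.

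**The Abstract's frequency-and-percentage rule already covers anti-D.** It yields a proportion, and the safety set supplies a population. It does not yield an interval, a rule for who is evaluable, or a comparison.

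**Historical controls can mislead.** They can; hence the labelling and the limitation in the fix.

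**Conclusion.** The concern holds. The 2000 figure is stated without inputs and does not follow from 22.9% against any DEL rate from 0 to 5%: equal groups need 30 to 58 each at 80% power and 39 to 77 at 90%. The multiple of 34 to 67 rests on my choice of alpha, power, DEL rate and allocation. The conclusion for 22.9% survives every variation tried; only the 8.5% against 5% contrast, with few controls per case, passes 2000.

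The reporting gap is separate and does not depend on those assumptions. Section XII(II) gives the first-listed safety index no specific summary, evaluable denominator, interval or historical comparison, so 0% could stand for an upper bound of 21.8% or of 6.0%.

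This should be fixed, though it does not undermine the trial. A small sample supports only a crude comparison with a pooled historical rate and cannot by itself establish a very low risk.

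**What to change.** 1. **Section III.** Delete the figure, or replace it with a calculation that states alpha, power, assumed DEL rate, control rate and design. Do not use it as the reason for omitting a historical comparison.
2. **Section XII(II), before lock.** Report anti-D incidence with a defined evaluable denominator (for example, safety-set patients with at least one post-transfusion antibody screen) and an exact Clopper-Pearson 95% CI. Show it beside 53/231 = 22.9% (exact 95% CI 17.7% to 28.9%), labelled a non-randomised historical comparison. If a test is wanted, prespecify one: Fisher's exact test against 53/231, which allows for uncertainty in the benchmark.
3. **Interpretation.** State that a rate below 22.9% does not by itself settle whether these patients are handled as D+ or D-, and that the upper bound is the key result.
4. **Limitation.** Note that the titles of references [19] and [20] name immunosuppressed oncology patients and AIDS patients, groups that exclusion criterion 2 keeps out of this trial.

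The cost is a few lines of text and SAS code, with no change to visits, sampling or recruitment. With no fixed N the interval may be wide, and a historical comparison can be over-read; the label and the limitation are there for that reason.

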4. The subject get Lost for follow-up after receiving transfusion treatment;
5. The data of the CRF table is incomplete or cannot be traced to the source, which affects the evaluation of efficacy and safety.

(V) Criteria for termination of the clinical trial

Study termination means that the clinical study has not been completed as planned, and all studies have been stopped halfway. The purpose of the study termination is to protect the rights and interests of the subjects, ensure the quality of the trial, and avoid unnecessary financial losses.

1. Serious safety problems occurred during the study, and the study should be suspended timely;
2. It is found that there are major mistakes in the clinical protocol in the study, and it is difficult to evaluate the treatment effect;
3. The research was stopped due to the requirements for funding and management;
4. The administrative department revokes the test, etc.;

When this occurs, the investigator needs to inform the subjects before stopping the trial.

V. Experimental intervention

When any hospital in Guangzhou city applies for D- blood supply in a non-emergency situation, the application and the patient's blood sample will be sent to the Reference laboratory of Guangzhou Center for "Asia type" DEL routine testing. For the "Asia type" DEL patients identified, the patients who meet the inclusion criteria will be enrolled in the hospital. After the patient or family members signed the informed consent for blood transfusion treatment, the matching D+ blood will be provided by Guangzhou Blood Center. According to the clinical blood transfusion guidelines, the blood transfusion for "Asia type" DEL patients was conducted in the corresponding hospital. According to *the Technical Specifications for Clinical Blood Transfusion*, the registration of

blood out-put and in-put, checking, and issuing should be carefully done in the blood transfusion departments or blood banks of all participating hospitals and the blood should be stored and transported in the temperature of 4 ± 2 ° C.

1. Before blood transfusion, two medical staffs should check the cross-matching report, the label of the blood bag, and check whether the blood bag is damaged or leaking and whether the blood color is normal. When all of these have been confirmed to be normal, the transfusion could start.

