It is necessary to monitor and record the occurrence of the adverse events and its development in detail throughout the clinical trial.

(IV) Observation index of curative effects

To record the changes in hemoglobin concentration and hematocrit before and after blood transfusion.

(V) Concomitant treatment

During the study, all concomitant treatments or combined medications (from the beginning of the signed informed consent to the end of the trial) must be recorded in detail in the original medical record, including the intervention name, intervention purpose, dosage form, single dose, dosage unit, frequency of use, route of administration, start date, end date, and whether it is still being used.

For the combined treatment in the clinical research process, the corresponding analysis and recording should be done, especially the combined treatment in the event of adverse events, recorded and reported in a timely manner.

VII. Evaluation Index

(I) Main indicators for evaluation of the effectiveness

Hemoglobin concentration and hematocrit.

(II) The indicators for evaluation of the safety of the trial

1. Incidence of anti-D alloimmunization;
2. Transfusion r adverse reaction;
3. Vital signs: temperature, heart rate, breathing, blood pressure;

4. Blood routine (WBC, NEUT, Hb, Hct, PLT), renal function (Urea, Cr), liver function (ALT, AST, TBIL, DBIL, TP, ALB), electrolytes (K^+ , Na^+ , Ca^{2+} , P^{3+} , Mg^{2+}) before and after transfusion;
5. Incidence and severity of adverse events.

VIII. Steps of Clinical trial

(I) Phase I of Visiting: -7 ~ 0 days before transfusion

1. To explain the research purpose, methods, and requirements to the subjects, and to sign the informed consent for blood transfusion treatment by the two parties jointly;
2. To Collecting the demographics, characteristics, past/concomitant medical history of the subjects, and to conduct detailed physical examinations, and measure vital signs (including heart rate, breathing, blood pressure, body temperature; to measure blood pressure in a resting state);
3. Laboratory testing:
 - 1) "Asia type" DEL typing;
 - 2) Cross-matching test (only for the "Asia type" DEL patients);
 - 3) Blood routine: white blood cells (WBC), neutrophils (NEUT), hemoglobin (Hb), hematocrit (Hct), platelets (PLT);
 - 4) Four items for infections detection;

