 - 5) Liver function testing: alanine aminotransferase (ALT), aspartate aminotransferase (AST), total bilirubin (TBIL), direct bilirubin (DBIL), total plasma protein (TP), plasma albumin (ALB);
 - 6) Renal function testing: Urea, creatinine (Cr);
 - 7) Examination of coagulation function: prothrombin time (PT), activated partial thromboplastin time (APTT), thrombin time (TT), fibrinogen (FIB);
 - 8) Urine routine;
 - 9) Stool routine, occult blood test;
 - 10) Pregnancy test: The women patients who reach menopause, or are undergoing menstruation at the time of the test, or have undergone birth control surgery do not need to have a pregnancy test, but need to record the reason for not doing so.
 - 11) Electrocardiogram.
4. Combined treatment/medication;
5. Evaluation of the patients for participation of this study based on inclusion and exclusion

criteria.

(II) Phase II of Visiting: Blood transfusion treatment period (0~1 days)

1. To record the detail of transfusion, including the time of transfusion start and end, the type of transfusion, the volume of transfusion, and to observe the adverse reaction during the transfusion treatment;
2. Observation of vital signs: temperature, heart rate, breathing, blood pressure;
3. Observation and recording of adverse events;
4. Combined treatment/medication.

(III) Phase III of Visiting: 1 day to 1 month after blood transfusion

1. Physical examination, observation of vital signs (including heart rate, breathing, blood pressure, body temperature and to measure blood pressure in a resting state);
2. Laboratory testing:
 - 1) Detection of anti-D immune response (using antibody screening test);
 - 2) Blood routine: including white blood cells (WBC), neutrophils (NEUT), hemoglobin (Hb), hematocrit (Hct), platelets (PLT);
3. Observation and recording of adverse events;
4. Combined treatment/medication.

(IV) Phase IV of Visiting: 1 month to 12 months after blood transfusion

1. Laboratory testing:
 - 1) Detection of anti-D immune response (using antibody screening test);
 - 2) "Asia type" DEL blood group typing.
2. Observation and recording of adverse events.

(V) Phase V of Visiting: Over 12 months after blood transfusion

1. Laboratory testing:
 - 1) Anti-D immune response test (using antibody screening test);
 - 2) "Asia type" DEL blood group typing.
2. Observation and recording of adverse events.

IX. Adverse events, serious adverse events

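### Minor: dropout criterion 3 removes adverse-event dropouts from the efficacy evaluation even when their haemoglobin and haematocrit pair is already complete, and nothing in section XII overrides it

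*Combined protocol and SAP*

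**What the plan says.** Section IV(IV), criterion 3, covers subjects whose adverse event stops them from completing the trial. On their analysis it says: "Cases dropout due to adverse events should be included in the statistical analysis of adverse events, but were not included in the evaluation of efficacy".

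The effectiveness indicators in section VII(I) are "hemoglobin concentration and hematocrit", and section VI(IV) gives the task as "To record the changes in hemoglobin concentration and hematocrit before and after blood transfusion".

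Section VIII and the flow chart in section XV place the blood routine, which contains Hb and Hct, at two visits only: Phase I (up to 7 days before transfusion) and Phase III, headed "Phase III of Visiting: 1 day to 1 month after blood transfusion". Follow-up continues through Phase IV to "Phase V of Visiting: Over 12 months after blood transfusion", and neither of those later visits schedules a blood routine.

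The other dropout criteria do not settle the analysis of their cases. Criteria 1 and 2 (follow-up not completed, withdrawal on request) and criterion 4 ("The subject get Lost for follow-up after receiving transfusion treatment") say nothing about it. Criterion 5 concerns case report data that are incomplete or untraceable to an extent that affects the efficacy and safety evaluation.

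Section XII(I) names a safety set, defined as everyone transfused at least once, and a full analysis set with no definition. Section XII(II) assigns the full analysis set to demographic and baseline data and the safety set to safety, and contains no effectiveness analysis.

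**The concern.** Whether a patient stays in the efficacy evaluation depends on something that happens after the intervention and possibly long after the outcome was measured. A subject sampled at Phase III who leaves in Phase IV or V because of an adverse event has supplied everything the Hb/Hct comparison needs, yet criterion 3 takes that subject out. If such patients had a different Hb rise from the rest, the reported mean rise does not describe the transfused patients with data.

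Effectiveness is part of the stated purpose in section II, and the blood group is rare enough that the sample size entry in the Protocol Abstract asks for as many cases as can be found. Discarding usable pairs works against that. Because section XII gives no effectiveness population, criterion 3 is the only instruction an analyst would have for these cases.

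**Working it through.** The plan gives no figure to reproduce: it has no adverse-event dropout rate, no expected Hb rise and no SD. The check is therefore a comparison of rule and schedule, followed by an illustration on assumed values.

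**Rule against schedule**

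| Visit | Hb/Hct scheduled | Dropout for an adverse event afterwards |
|---|---|---|
| Phase I, before transfusion | yes | no post-transfusion value yet |
| Phase II, day 0 to 1 | no | no scheduled post-transfusion value yet |
| Phase III, 1 day to 1 month | yes | pair complete once sampled, still excluded |
| Phase IV, 1 to 12 months | no | pair complete if sampled at Phase III, still excluded |
| Phase V, beyond 12 months | no | as Phase IV |

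The rule discards data only for patients who leave after the Phase III sample. Those who leave earlier have no scheduled pair to lose.

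**Size among patients with a pair**

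Let p be the fraction of pairs removed by criterion 3, and d the mean rise in those kept minus the mean rise in those removed.

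- Mean over all pairs = (1 − p) × mean kept + p × mean removed.
- Reported mean = mean kept.
- Bias = mean kept − mean over all pairs = p × d.

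p is not the dropout rate. With a = fraction of transfused patients who drop out for adverse events, q = share of those with a pair, and k = share of the remaining patients with a pair:

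p = aq / (aq + (1 − a)k)

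All of a, q, k and d are assumptions. With k = 1:

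| a | q | p | Bias at d = −10 / 0 / +10 g/L |
|---|---|---|---|
| 5% | 0 | 0 | 0 / 0 / 0 |
| 5% | 0.5 | 0.025/0.975 = 2.6% | −0.26 / 0 / +0.26 |
| 5% | 1 | 5% | −0.50 / 0 / +0.50 |
| 10% | 0 | 0 | 0 / 0 / 0 |
| 10% | 0.5 | 0.05/0.95 = 5.3% | −0.53 / 0 / +0.53 |
| 10% | 1 | 10% | −1.00 / 0 / +1.00 |

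With k = 0.9, a = 10% and q = 0.5, p = 0.05/0.86 = 5.8%, and the bias at d = 10 is 0.58 g/L.

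**The case against.** The strongest reply is that little is lost. Section VII(II) also lists Hb and Hct before and after transfusion among the safety indicators. Section XII(II) describes blood-routine values and changes in the safety set, that is, in everyone transfused. An excluded patient's Hb change therefore still appears in the report. This stands, and it is the main reason why the point is minor. It does not remove the point, because the report could carry two Hb changes on different patients, with the one labelled efficacy being the selected one.

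Two further replies also stand. The analysis is descriptive, and no test or decision threshold uses the mean Hb rise; the aim stated in section III is anti-D alloimmunization, which criterion 3 does not touch. The illustrated shift is also small against sampling error: on further assumptions (30 to 100 patients, SD 10 to 20 g/L) the standard error of the mean rise runs from 10/√100 = 1.0 to 20/√30 = 3.7 g/L.

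A reader might infer that adverse-event dropouts alone are removed while all other dropouts are kept. The documents do not support this. Criteria 1, 2 and 4 are silent, which does not show that their cases are retained, and criterion 5 may also lead to cases being left out of efficacy.

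**Conclusion.** The point holds as a minor one. Read as written, criterion 3 can remove complete Hb/Hct pairs because of a later adverse event, and section XII provides nothing that overrides it. The lack of a definition for the full analysis set would by itself be missing detail; it matters here because it leaves criterion 3 in force for effectiveness.

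The size of any bias is p × d. It is zero if no excluded patient has a pair or if the excluded patients had the same mean rise as the rest. On the assumed ranges it does not exceed 1.0 g/L in either direction.

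A reader might infer that the rule makes the transfusion look more effective than it was. The documents do not support a direction: unrelated events also trigger the exclusion, and nothing links an event months later to the Hb rise measured at Phase III. Nor is there any consequence for the anti-D result.

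**What to change.** 1. In section IV(IV), delete the closing clause of criterion 3, which takes adverse-event dropouts out of the efficacy evaluation. Their inclusion in the adverse-event analysis stays as it is.
2. In section XII, add an effectiveness summary of Hb and Hct change. It should cover every transfused subject with a pre-transfusion value and a Phase III value, whatever happens later, and use the first Phase III value if there are several. Naming the value matters because section VI(III) allows repeat tests.
3. In the same place, report how many transfused subjects lack a Phase III value and the reasons.

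Section XI(II) fixes the statistical plan at data lock, so the change has to be made before then.

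The cost is a few lines of protocol and analysis wording and slightly more analysis work. No extra tests or visits are needed. The mean rise may move slightly in either direction.
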